7.2 GENERAL CRITERIA

- Inability of subject to comply with study requirements
- Determination by the investigator that it is no longer safe for the subject to continue therapy

8. CRITERIA FOR STUDY DISCONTINUATION

Treatment will continue for six cycles of combination therapy and 12 cycles (2 years) of maintenance obinutuzumab as per study design, or until the occurrence of any of the following events.

Treatment with study drug is to be discontinued when any of the following occurs:

- Lack of therapeutic effect
- Adverse event(s) that, in the judgment of the Investigator, may cause severe or permanent harm or which rule out continuation of study drug.
- Major violation of the study protocol.
- Withdrawal of consent
- Lost to follow up
- Death
- Suspected pregnancy

9. CLINICAL AND LABORATORY EVALUATIONS

9.1 PRETREATMENT EVALUATIONS

Please see schedule of study assessments for screening evaluations (section 2.1). Screening evaluation will be performed within 30 days of study entry. In the absence of a history of blood transfusion or intravenous drug use in the past 6 months, patients can have hepatitis B/C and HIV testing up to 8 weeks prior to study entry.

9.2 EVALUATIONS DURING TREATMENT

Patients will undergo tumor response assessment including a CT scan of the neck, chest, abdomen, and pelvis, physical exam, and basic laboratory panel during screening, after 3 and 6, 9 and 12 cycles of combination treatment, and every 4 months during maintenance phase with obinutuzumab.

9.3 POST-TREATMENT EVALUATIONS

Subjects who discontinue treatment for any reason, other than completion of therapy, will be followed for a minimum of 6 months from last dose of drug. Subjects will undergo a safety assessment approximately 28 days post the last dose of study drug. In addition, off study evaluations, such as recording subsequent therapy, per the Schedule of Assessments will be done. Following completion of chemotherapy, patients will be evaluated every 3 months for one year, every 6 months for 1 year and then yearly with CT of neck, thorax, abdomen and pelvis and other studies as recommended by the treating physician. When patient starts alternative treatment for lymphoma, they will no longer be followed pre protocol.

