2. STUDY DESIGN

2.1 SCHEDULE OF STUDY ASSESSMENTS

		SCHEDULE OF STUDY ASSESSMENTS								
Procedure 8*	Screening ≤ 30days from Baseline (First day study drug administration)	Cycle 1				All Cycles *	All Cycles *	Following Cycles 3, 6, 9 ¹³ , 12 ¹³ then every 4 months during obinutuzumab maintenance* ¹⁵	Discontinuation From Study Drug	Follow-Up Phase
		Day 1	Day 8	Day 15	Day 22	Day 1	Day 14			
Record prior medications, treatments	X									
Record prior anti-cancer therapies	X									
Medical History	X	X				X				
HTLV1, HIV and Hepatitis B/C screening ¹⁰	X									
Physical examination, vital signs, weight	X	X				X			X	
ECOG performance status	X	X				X			X	
CT of the chest & abdomen / pelvis, neck, PET CT. ^{8*}	X							X	X	X ⁶
Chest x-ray	X								X	
Electrocardiogram (EKG)	X									
Bilateral bone marrow Bx, BM cytogenetics. On Follicular lymphoma histology do BM and blood PCR for Bcl-2 rearrangement. On SLL do ZAP70, CD38 staining and somatic mutation analysis on BM and tumor tissue.	X ²							X ²	X ²	

2013-0261 - Obinutuzumab Plus Lenalidomide in Low Grade Lymphoma

Register patient into Revlimid REMS® program ¹	X										
Prescribe lenalidomide via Revlimid REMS® program ¹	X					X					
obinutuzumab infusion ^{12,14}		X	X	X	X	x ¹²					
Hematology Test: hematocrit, platelet count, WBC count with differential, Absolute neutrophil count (ANC) and absolute lymphocyte count (ALC). ^{9, 11}	X	X	x	X	X	x ¹¹	X			X	
Serum chemistry: Blood chemistries should include sodium, potassium, chloride, CO ₂ , blood urea nitrogen (BUN), creatinine, glucose, aspartate aminotransferase (AST), alanine aminotransferase (ALT), total bilirubin, alkaline phosphatase, lactate dehydrogenase (LDH), calcium, ⁵	X	X	X	X	X	X	X			X	
Pregnancy test ^{3,4}	x ⁴	X	X	X	X	X	4			X	4
Tumor lesions assessment	X								X	X	x ⁶
Response assessment using IWG criteria									X	X	
Record concomitant therapies/procedures	x					X				X	
Obtain Follow-Up anti-cancer treatments										X	x ⁶
Obtain Follow-Up survival information											x ⁶

* Variations of +/- 3 days of the schedule are permitted.

** Staging CTs and BM Bx will be done up to 7 days of end of cycle

2013-0261 - Obinutuzumab Plus Lenalidomide in Low Grade Lymphoma

1. Lenalidomide must be prescribed through and in compliance with Celgene's Revlimid REMS® program. Prescriptions must be filled within 7 days.

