2. Repeat BM evaluation to confirm morphologic and genetic markers of disease. Zap 70 and CD38 staining will be done if tissue is available. Repeat BM biopsy is at investigators discretion to confirm complete remission (as determined by radiographic imaging). Screening bone marrow biopsy can be obtained up to 60 days prior to study entry.
3. Pregnancy tests for females of childbearing potential. A female of childbearing potential (FCBP) is a sexually mature female who: 1) has not undergone a hysterectomy or bilateral oophorectomy; or 2) has not been naturally postmenopausal for at least 24 consecutive months (i.e., has had menses at any time in the preceding 24 consecutive months).
4. Pregnancy tests must occur within 10 – 14 days and again within 24 hours prior to prescribing lenalidomide (prescriptions must be filled within 7 days). FCBP with regular or no menstruation must have a pregnancy test weekly for the first 28 days and then every 28 days while on therapy (including breaks in therapy), at discontinuation of lenalidomide and at Day 28 post the last dose of lenalidomide. Females with irregular menstruation must have a pregnancy test weekly for the first 28 days and then every 14 days while on therapy (including breaks in therapy), at discontinuation of lenalidomide and at Day 14 and Day 28 post the last dose of lenalidomide (see Appendix: Risks of Fetal Exposure, Pregnancy Testing Guidelines and Acceptable Birth Control Methods).
5. Thyroid Stimulating Hormone (TSH) will be drawn at baseline and prior to cycles 4
6. Follow-up and tumor assessment – Patients will be evaluated every 3 months for one year, every 6 months for 1 year and then yearly with CT of neck, thorax, abdomen and pelvis and other studies as recommended by the treating physician for 1 year. Timing of imaging studies will be calculated from date of last scan. Tumor assessments, as well as timeline for tumor assessments are recommendations only. Exact timing of follow-up tumor assessments are at the discretion of the treating physician. Patients will have a minimum of imaging studies every 6 months for the first. Imaging can be done plus/-21 days of recommended time points.
7. Patient evaluation and predose labs can occur up to 3 days prior to starting each cycle. If possible, patients should be seen at least 24 hours prior to each cycle

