2.2.2 Secondary Objectives

1. To determine the complete response rate, time to progression (TTP), and progression free survival in patients with indolent lymphoma following treatment with obinutuzumab + lenalidomide.
2. To evaluate changes in immune effector cells and the tumor microenvironment following treatment with obinutuzumab + lenalidomide.

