2.3.3 Phase II

The objective for the phase II part is to further evaluate the safety and efficacy of lenalidomide when given in combination with obinutuzumab at the MTD of lenalidomide determined in phase I. The maximum number of patients that will be recruited for the phase II part is 60 with 30 for each of the two patient cohorts: the patients with follicular lymphoma (grade 1-3a) and the patients with any indolent lymphoma. The patients who are treated at the MTD in the phase I part will be counted as the first group of patients treated in phase II.

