6.4 DISCONTINUATION OF STUDY TREATMENT

Follow-Up

Subjects who discontinue treatment, will be followed for a minimum of 6 months. Patients who die or withdraw consent will not be followed beyond the date of the death or withdrawal of consent. Patients who start alternative therapy will not be followed beyond initiation of next line therapy except for survival. All other patients that remain on study (ie completion of therapy, or drug interruption due to toxicity) will be followed with tumor lesion assessments, imaging, and survival per the schedule of assessments, Section 2.1. Subjects will undergo a safety assessment approximately 28 days post the last dose of study drug. In addition,

off study evaluations, such as recording subsequent therapy, per the Schedule of Assessments will be done. Following completion of chemotherapy, patients will be evaluated every 3 months for one year, then every 6 months for a total of 2 years following completion of therapy with CT of neck, thorax, abdomen and pelvis and other studies as recommended by the treating physician.

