11.2 Analysis Plans

Phase I:

Toxicity type and severity by dose level will be summarized using frequency tables.

Phase II:

The analysis for phase II will include the patients who are treated at the MTD in phase I.

Toxicity type and severity will be summarized for each patient cohort using frequency tables.

Summary statistics will be provided for continuous variables. Frequency tables will be used to summarize categorical variables. The overall response rate for each patient cohort will be calculated and the Clopper Pearson confidence interval will be provided. Chi square test or Fisher's exact test will be used to evaluate the association between patient prognostic factor and response. The distribution of time-to-event endpoints including overall survival and progression free survival will be estimated using the method of Kaplan and Meier.

Comparison of time-to-event endpoints by important subgroups will be made using the log-rank test.

For the toxicity endpoint, per-treated analysis will be performed to include any patient who received the treatment regardless of the eligibility nor the duration or dose of the treatment received. For the efficacy endpoints, intend-to-treat analysis will be applied to the eligible patients.

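### Sections 6.4 and 9.3 contradict each other on survival follow-up after next lymphoma therapy; applied literally, 9.3 could bias the descriptive overall survival curve upward

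*Combined protocol and SAP*

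**What the plan says.** Two sections of the protocol say what happens when a patient starts another lymphoma treatment.

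- Section 6.4 (Discontinuation of study treatment): "Patients who start alternative therapy will not be followed beyond initiation of next line therapy except for survival".
- Section 9.3 (Post-treatment evaluations): "When patient starts alternative treatment for lymphoma, they will no longer be followed pre protocol". The word before the last is presumably a slip for per.

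The schedule in section 2.1 has a follow-up row, "Obtain Follow-Up survival information", tied to footnote 6. That footnote begins "Follow-up and tumor assessment – Patients will be evaluated every 3 months for one year, every 6 months for 1 year and then yearly" and deals with visits and imaging. It does not say whether survival contact goes on after next therapy.

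Section 11.2 states: "The distribution of time-to-event endpoints including overall survival and progression free survival will be estimated using the method of Kaplan and Meier". It adds: "Comparison of time-to-event endpoints by important subgroups will be made using the log-rank test". It gives no censoring rule for OS. OS is not among the objectives; the secondary ones begin "To determine the complete response rate, time to progression (TTP), and progression free survival in patients with indolent lymphoma".

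**The concern.** Kaplan-Meier estimation needs patients censored at a given time to have the same outlook as those still followed. Starting another lymphoma treatment usually means that the disease has progressed or responded too little. Section 1.1.2 itself describes relapses that grow more resistant with each line of therapy, and death from recurrent disease or treatment toxicity. Ending follow-up at next therapy would therefore tend to remove the patients at higher risk of death, and leave the OS curve resting on those doing better. The subgroup log-rank tests would use the same data.

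The study has no concurrent control that would show up an inflated curve. The loss would also arise at data collection: if vital status after next therapy is not gathered, an analyst may be unable to recover it.

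**Working it through.** **Step 1: the text.** Does survival follow-up continue after next therapy?

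| Place | Answer |
|---|---|
| 6.4 | Yes, by explicit exception |
| 9.3 | No exception stated |
| 2.1, survival row | Collected in the follow-up phase; silent on next therapy |
| 2.1, footnote 6 | Visit and imaging timing only; silent |
| 11.2 | OS to be estimated; no censoring rule |

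The first two rows conflict, and none of the others resolves them.

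**Step 2: what each rule does to OS.** The plan states no OS rate, event count or precision, so there is no figure of its own to reproduce. All rates below are assumptions. Let

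- λ = rate of starting next therapy = ln 2 / median time to it (in years), taken as exponential;
- h0 = death hazard before next therapy = 0.02 per year;
- h1 = death hazard after it = 0.02, 0.04 or 0.10 per year.

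Under 6.4 the curve estimates true survival. At 3 years, with k = h0 + λ − h1,

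S(3) = exp(−3(h0 + λ)) + (λ/k) · exp(−3·h1) · (1 − exp(−3k)).

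Under 9.3 read literally, only the earlier hazard is seen, and the curve tends to exp(−3·h0) = exp(−0.06) = 94.2%.

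**Step 3: median 24 months.** λ = 0.6931/2 = 0.3466. The first term is exp(−1.0997) = 0.3330.

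- h1 = 0.02: k = 0.3466; second term 1 × 0.9418 × 0.6464 = 0.6088; S(3) = 94.2%. Bias 0.
- h1 = 0.04: k = 0.3266; second term 1.0612 × 0.8869 × 0.6246 = 0.5879; S(3) = 92.1%. Bias 2.1 points.
- h1 = 0.10: k = 0.2666; second term 1.3001 × 0.7408 × 0.5505 = 0.5303; S(3) = 86.3%. Bias 7.9 points.

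The share of patients who start next therapy by 3 years is λ/(λ + h0) × (1 − exp(−3(λ + h0))) = 0.9454 × 0.6670 = 63%.

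**Step 4: range of medians.** Bias in 3-year OS, in percentage points:

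| Median to next therapy | h1 = 0.02 | h1 = 0.04 | h1 = 0.10 |
|---|---|---|---|
| 18 months | 0 | 2.5 | 9.5 |
| 24 months | 0 | 2.1 | 7.9 |
| 36 months | 0 | 1.5 | 5.8 |

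**Step 5: a second model.** A simulation separated progression from next therapy. It assumed median progression at 18 to 36 months, 60% or 90% of progressors starting next therapy 0 to 6 months later, and a death hazard of 0.01 or 0.03 per year before progression. With 0.10 to 0.30 per year after progression, 3-year OS was too high by about 2 to 17 points. With equal hazards there was no bias, but deaths were still lost: for example 0.8 instead of 1.5 per 30 patients by 5 years (median 24 months, hazard 0.01, 90% starting next therapy). The direction agrees with steps 3 and 4; the size depends on the rates assumed.

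**The case against.** The best defence is that 9.3 can be read in harmony with 6.4. The sentence closes a section on post-treatment evaluations and directly follows the CT timetable, so it may end only those evaluations. Section 6.4 is explicit, and the schedule has a survival row. This is a fair reading, and it makes the remedy a clarification rather than a change of design. But 9.3 does not say so, and survival contact is itself a scheduled item, so staff who work from 9.3 could reasonably stop it.

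Second, OS is a minor endpoint and the bias may be lost in noise. Phase II has at most 30 patients per cohort ("The maximum number of patients that will be recruited for the phase II part is 60 with 30 for each of the two patient cohorts"). At 92.1% survival the binomial standard error is √(0.921 × 0.079/30) = 4.9 points, or 3.5 with 60 patients, so a bias of 2.1 points is below one standard error. At 86.3% it is √(0.863 × 0.137/30) = 6.3 points, and a bias of 7.9 exceeds it. The objection therefore stands for the milder case only. Random error also differs from a shift that always runs one way.

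Third, a reader might infer that the plan has chosen to censor OS at next therapy, so that the reported curve is bound to be biased. The documents do not support that. Section 11.2 sets no such rule, 6.4 points the other way, and bias needs two conditions: that 9.3 is followed over 6.4, and that the death hazard rises after next therapy.

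**Conclusion.** The contradiction is certain from the text; a biased OS result is only possible. If 9.3 is applied literally and the death hazard is higher after next therapy, OS is biased upward. On the assumed rates, the 3-year bias is 1.5 to 2.5 points at 4% per year afterwards, 5.8 to 9.5 points at 10%, and zero if the hazard stays at 2%. None of these rates comes from the documents.

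A reader might also take this as a threat to the trial's main conclusions. It is not. MTD, safety, overall response rate and the stopping rules do not use OS. Both sections end tumour assessment at next therapy, so the conflict does not affect PFS or TTP. What is exposed is one descriptive curve outside the listed objectives, with its subgroup tests. The wording still deserves correction, because deaths that were never collected may not be recoverable at analysis.

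**What to change.** Amend 9.3 to match 6.4: tumour assessments end when another lymphoma treatment starts, while survival status is collected until death, withdrawal of consent or study close. Repeat this in footnote 6 of the schedule, which is silent on it. In 11.2, state that patients not known to have died are censored for OS at the date last known alive, and that starting another therapy is not a censoring event for OS.

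The cost is one or two sentences of amendment, plus continued survival contact, which 6.4 already requires. No treatment, visit or imaging rule changes.

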10. EVALUATION OF RESPONSE

Response criteria for patients enrolled onto the study will follow the guidelines recommended by the 1999 International Workshop on Response Criteria for NHL (Cheson et al. 1999). All responses will be characterized as either complete remission (CR), unconfirmed complete remission (CRu), partial remission (PR), stable disease (SD), or progression of disease (POD). Response will be assessed after every three cycles of therapy and at the completion of lenalidomide treatment. Response will be assessed every 4 months thereafter while the patient receives obinutuzumab.

11. STATISTICAL CONSIDERATIONS

This is a single-center, open label, phase I/II study in patients with refractory or relapsed indolent lymphoma. The feasibility of administrating lenalidomide in combination with obinutuzumab and the MTD of the combination will be determined in the phase I part of the study. When the MTD has been established, the efficacy of the combination will be further evaluated in the phase II part of the study in two patient cohorts simultaneously. The two patient cohorts are the patients with follicular lymphoma (grade 1-3a) and the patients with either follicular lymphoma, marginal zone lymphoma, or SLL. A maximum of 72 patients (18 in phase I and 60 in phase II (30 patients each cohort); the patients treated at the MTD in phase I will be counted as the first group of patients treated in phase II) will be enrolled in this study on an intent-to-treat basis.

11.1 STATISTICAL/STUDY DESIGN

11.1.1 Phase I

The primary objective of the phase I part of the study is to determine the maximum tolerated dose (MTD) of lenalidomide when given in combination with obinutuzumab for subsequent testing in the phase II part of the trial. There are three predefined dose levels for lenalidomide (10 mg, 15 mg, 20 mg) with a fixed dose of obinutuzumab (1000mg) as outlined in Table 2.

Dose limiting toxicity (DLT) will be assessed during the first course of each cohort (28 days), and refers to a medically significant event which meets one of the following criteria using National Cancer Institute Common Terminology Criteria for Adverse Events (NCI CTCAE) version 4:

- Grade 3 or higher non-hematologic AE which is felt to be related to the study drug by the investigator with the exception of the following:
- Transient grade 3 or more infusion reaction that completely resolves within 24 hours.
- Grade 4 hematologic toxicity (Platelet count is defined as <25,000 for the purposes of determining DLT).
- Grade 3 neutropenia with elevated temperature (defined as >= 101 degrees F to be confirmed on two occasions).
- Grade 3 thrombocytopenia with bleeding.
- Treatment delay of greater than 2 weeks due to treatment related toxicity.

The target rate of DLT is 30%. The standard '3+3' design will be used. Applying the 3+3 design, the first cohort of 3 patients will be treated at dose level 1 and evaluated at the end of 28 days. The algorithm is as follows: (1) If 0 out of 3 patients experiences DLT, the next cohort of 3 patients will be

~~2013-0261: Obinutuzumab Plus Lenalidomide in Low Grade Lymphoma~~

treated at the next higher dose level. (2) If 1 out of 3 patients develop DLT, additional 3 patients will be treated at the same dose level. If no more DLT develops at the dose, i.e. 1 out of a total of 6 patients develops DLT, the dose escalation continues for the next cohort of 3 patients. (3) At any given dose, if greater than 1 out 3 patients or 1 out of 6 patients experience DLT, the dose level exceeds the MTD and 3 more patients will be treated at the next lower dose if there are less than 6 patients already treated at that dose. Following the above scheme, MTD is defined as the highest dose level in which 6 patients have been treated with less than 2 instances of DLT. Given 3 dose levels, it is anticipated that up to 18 eligible patients are required for the phase I part of the study.

Safety parameters and DLTs will be summarized and listed by each dose level.

Prior to advancing/changing dose levels a cohort summary will be completed and submitted to the Clinical Research Monitor in the IND Office.

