Study BO21000 is an ongoing, open-label, randomized Phase I/II trial investigating two doses of obinutuzumab (400 mg in all cycles and 1600 cycle 1/800 mg subsequent cycles) in combination with chemotherapy given every 4 weeks for a maximum of six cycles (obinutuzumab plus fludarabine and cyclophosphamide [G-FC]) or a maximum of eight cycles (obinutuzumab plus CHOP [G-CHOP]) in patients with relapsed or refractory follicular lymphoma. Patients with a PR or CR who complete a minimum of four cycles of G-FC or six cycles of G-CHOP have the option of receiving maintenance therapy with obinutuzumab alone every 3 months for up to 2 years. All patients (28/28) who received G-CHOP and 22/28 who received G-FC completed treatment. Reasons for withdrawal from the G-FC arm were PD (1 patient), neutropenia (3 patients) and rash and infection (1 patient each) (Radford et al. 2011)

Overall, the rate of adverse events was similar between the high-dose and low-dose arms. The most common AE in both groups was IRRs, mostly during cycle 1. The rate of IRRs was 64% of patients in the G-CHOP arm and 79% of patients in the G-FC arm; 7% of IRR events were Grade 3 or 4 events in both chemotherapy arms. There were fewer dose delays, dose reductions, and neutropenia in the G-CHOP versus the G-FC cohorts. Grade 3/4 neutropenia was seen in 39% of the G-CHOP patients and 50% of the G-FC patients. In the G-CHOP arm 6% of cycles were delayed due to neutropenia or infection and the dose of any CHOP component was reduced in 29% of patients. In the G-FC arm, 10% of cycles were delayed due to neutropenia or infection with dose reductions

in 36% of patients. Three deaths were reported following G-FC induction treatment (progressive disease, n=1; underlying Parkinson's disease, n=1; and chronic obstructive pulmonary disease during maintenance, n=1) with none considered to be treatment-related.

The overall response rate (ORR) at the end of induction was 96% in the G-CHOP group (39% CR) and 93% in the G-FC group (50% CR). Data from the G-CHOP cohort were compared in a matched-pair analysis to the rituximab plus CHOP (R-CHOP) arm from study M39022 (EORTC 20981) in a similar patient population. Response rates to G-CHOP compared favorably to response rates to R-CHOP.

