2.3.2 Phase I

The primary objective of the phase I part of the study is to determine the maximum tolerated dose (MTD) of lenalidomide when given in combination with obinutuzumab for subsequent testing in the phase II part of the trial.

There are three predefined dose levels for lenalidomide (10 mg, 15 mg, 20 mg) with a fixed dose of obinutuzumab (1000 mg) as outlined in Table 1.

Dose limiting toxicity (DLT) will be assessed during the first course of each cohort (28 days), and refers to a medically significant event which meets one of the following criteria using National Cancer Institute Common Terminology Criteria for Adverse Events (NCI CTCAE) version 4:

- Grade 3 or higher non-hematologic AE which is felt to be related to the study drug by the investigator with the exception of the following:
 - Transient grade 3 or less infusion reaction that completely resolves within 24 hours.
- Grade 4 hematologic toxicity (Platelet count is defined as <25,000 for the purposes of determining DLT).
- Grade 3 neutropenia with elevated temperature (defined as >= 101 degrees F to be confirmed on two occasions).
- Grade 3 thrombocytopenia with bleeding.
- Treatment delay of greater than 2 weeks due to treatment related toxicity.

Prior to advancing/changing dose levels a cohort summary will be completed and submitted to the Clinical Research Monitor in the IND Office.

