4. TREATMENT PLAN

4.1 Phase I

Three dose levels of lenalidomide (10 mg, 15 mg, 20 mg) will be evaluated with a fixed dose of obinutuzumab (1000mg) as outlined in Table 1. (obinutuzumab will be given in divided doses on cycle 1; 100mg IV on day 1, and 900mg IV on day 2, subsequent doses will be given over 1 day) Up to 18 patients may participate in the Phase I component of the study, depending on the level at which toxicity is observed. Subjects will be assigned to a dose level based on the order of study entry and toxicities seen in prior patients. The dose escalation process is described below. There will be no intra-patient dose escalation. DLT will be assessed during the first course of each cohort (28 days), and refers to a medically significant event which meets criteria using National Cancer Institute Common Terminology Criteria for Adverse Events (NCI CTCAE) version 4. (see section 2.3.2)

Table 1. Dose levels to be tested in phase I portion

Dose Level	Lenalidomide Dose (days 2-22 followed by 6 days of no therapy)	Obinutuzumab dose
-1	5 mg	1000mg IV
1	10 mg	
2	15 mg	
3	20 mg	

4. 2 Phase II

Additional pts will be enrolled into two cohorts at the recommended dose level (MTD) established in Phase I up to a maximum of 30 patients each in two independently enrolling cohorts.

Cohort A: 30 patients with relapsed/refractory follicular lymphoma

Cohort B: 30 patients follicular lymphoma, marginal zone lymphoma or SLL

[figure not shown]
4. 3 Treatment Schedule

Lenalidomide capsules will be taken orally daily each day on days 2 - 22, followed by 6 days of no therapy of each 28-day cycle. Obinutuzumab will be given by intravenous infusion on day 1,,2, 8, 15, and 22 of cycle one and on day 1 of each subsequent cycle up to 6 cycles. Patients who do not progress following 6 cycles and are deriving benefit from the combination in the opinion of the treating physician can receive further cycles of combination up to 12 cycles of lenalidomide therapy. (As long as the patient does not exhibit progression, the decision of how many cycles of combination therapy beyond 6 is at the discretion of the treating team and investigator).

Extended dosing of obinutuzumab will begin after combination therapy if patients demonstrate at least stable disease on response assessment. In the extended dosing schedule, obinutuzumab will be administered every 2 months, and in the absence of progression, will be dosed for maximum of 30 months (combination + maintenance).

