6.1.1 MANAGEMENT OF INFUSION-RELATED REACTIONS AND ANAPHYLAXIS

Medications (including epinephrine for subcutaneous injections, corticosteroids, diphenhydramine hydrochloride for IV injection) and resuscitation equipment should be available for immediate use at point of infusion. Management of infusion-related symptoms for obinutuzumab is summarized in Table 4. In the event of a life-threatening IRR (which may include pulmonary or cardiac events) or an IgE-mediated anaphylactic reaction, obinutuzumab should be discontinued and no additional drug should be administered. Patients who experience any of these reactions should receive aggressive symptomatic treatment and will be discontinued from study treatment.

Patients who experience obinutuzumab -associated, infusion-related temperature elevations of $>38.5^{\circ}\text{C}$ or other minor infusion-related symptoms may be treated symptomatically with acetaminophen (≥ 500 mg) and/or H₁- and H₂-histamine–receptor antagonists (e.g., diphenhydramine hydrochloride, ranitidine). Serious infusion-related events, manifested by dyspnea, hypotension, wheezing, bronchospasm, tachycardia, reduced oxygen saturation, or respiratory distress, should be managed with additional supportive therapies (e.g., supplemental oxygen, β_2 -agonists, epinephrine, and/or corticosteroids) as clinically indicated according to standard clinical practice.

Table 4

Guidelines for Management of Infusion-Related Symptoms Related to Obinutuzumab

Infusion-Related Symptoms ^a	Guidance
Grade 4	
 Discontinue infusion immediately, treat symptoms aggressively, and do not resume treatment.
Grade 3	
 Hold infusion. Give supportive treatment.^b Upon symptom resolution, may resume infusion rate escalation at the investigator's discretion.^c If the same adverse event recurs with the same severity, treatment must be permanently discontinued.
Grade 1–2	
 Slow or hold infusion. Give supportive treatment.^b Upon symptom resolution, may resume infusion rate escalation at the investigator's discretion.^c

^a Refer to National Cancer Institute Common Terminology Criteria for Adverse Events, Version 4.0 for the grading of symptoms. This table does not refer to management of immunoglobulin E-mediated allergic reactions, which should be managed as directed in Section 6.1.1.

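### Section 11.1.1 exempts a transient grade 4 infusion reaction from the DLT count, whereas section 2.3.2, the definition section 4.1 cites, counts it

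*Combined protocol and SAP*

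**What the plan says.** Sections 2.3.2 and 11.1.1 both list the DLT criteria. In both, the first criterion is a non-hematologic event of grade 3 or higher that the investigator judges related to study drug, subject to one exception for infusion reactions.

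- Section 2.3.2 excepts a "Transient grade 3 or less infusion reaction that completely resolves within 24 hours".
- Section 11.1.1 excepts a "Transient grade 3 or more infusion reaction that completely resolves within 24 hours".

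The remaining criteria match, including "Treatment delay of greater than 2 weeks due to treatment related toxicity". Section 11.1.1 then sets a 30% target DLT rate, the 3+3 steps, and the MTD as the highest dose at which six patients have had fewer than two DLTs.

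Two other places bear on which wording is meant. Section 4.1 sends the reader to section 2.3.2 for the DLT criteria. Table 4 in section 6.1.1 instructs for a grade 4 infusion reaction: "Discontinue infusion immediately, treat symptoms aggressively, and do not resume treatment". The text of 6.1.1 says of a life-threatening reaction that "obinutuzumab should be discontinued and no additional drug should be administered". Nothing says which section governs if the two lists conflict.

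**The concern.** One word decides whether a life-threatening but short-lived infusion reaction counts towards dose escalation. The wording that leaves it out stands in the section a statistician would apply, while the treatment plan directs clinicians to the wording that counts it. The same patient could therefore be classified in two ways.

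The rule works on three or six patients, so one reclassified event can change the decision. A count of 0/3 (escalate) becomes 1/3 (treat three more), and 1/6 (escalate) becomes 2/6 (dose exceeds the MTD). Section 11.1.2 also monitors DLT after cycle 1 in both phase II cohorts and gives no definition of its own, so the ambiguity carries over to that toxicity stop.

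**Working it through.** **Where the two lists differ**

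| Related infusion reaction resolving within 24 h | Section 2.3.2 | Section 11.1.1 |
|---|---|---|
| Grade 1–2 | not a DLT (below grade 3) | not a DLT (below grade 3) |
| Grade 3 | exempt | exempt |
| Grade 4 | DLT | exempt |

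A fatal reaction does not resolve, so the conflict is confined to grade 4.

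**Inputs.** No figure in the plan depends on this word, so there is none to reproduce for phase I. The documents give no grade 4 rate. The nearest figures are in section 1.2.3 (Study BO21000): infusion reactions in 64% and 79% of patients in the two chemotherapy arms, and "7% of IRR events were Grade 3 or 4 events in both chemotherapy arms". With one event per patient assumed, 0.64 × 0.07 = 4.5% and 0.79 × 0.07 = 5.5% of patients have grade 3 or 4 combined. **Assumption:** a transient grade 4 rate *g* of 1% to 2%, independent of other DLTs, which is between 0.01/0.0553 = 18% and 0.02/0.0448 = 45% of those reactions. The rate *o* of other DLTs is set at 10%, 20% and 30%.

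**Escalation past one dose level.** With DLT probability *p*, the 3+3 rule escalates with probability (1−p)³ + 3p(1−p)⁵. Under 11.1.1, p = o. Under 2.3.2, p = o + g(1−o).

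| o | 11.1.1 | 2.3.2, g = 1% | 2.3.2, g = 2% | Drop (points) |
|---|---|---|---|---|
| 10% | 0.906 | 0.891 | 0.875 | 1.5 to 3.1 |
| 20% | 0.709 | 0.691 | 0.674 | 1.7 to 3.5 |
| 30% | 0.494 | 0.480 | 0.466 | 1.4 to 2.8 |

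**Chance that the question arises.** At least one event in *n* patients has probability 1 − (1−g)ⁿ. For n = 12 (three, three, then six at the third level) this is 0.114 to 0.215; for the maximum of 18 it is 0.165 to 0.305. Exactly one event among the first three patients at a given level has probability 3g(1−g)² = 0.029 to 0.058.

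**When it does arise.** Suppose exactly one such event falls among the first three patients at a level and no grade 4 event follows. Under 11.1.1 it is ignored, and escalation keeps the probability (1−o)³ + 3o(1−o)⁵. Under 2.3.2 it uses up the one DLT allowed, so the other two patients and the next three must all be free of DLT: (1−o)⁵.

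| o | 11.1.1 | 2.3.2 |
|---|---|---|
| 10% | 0.906 | 0.590 |
| 20% | 0.709 | 0.328 |
| 30% | 0.494 | 0.168 |

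**Phase II.** The toxicity boundaries of 7, 11 and 15 DLTs at 10, 20 and 30 patients reproduce from the stated beta distributions and the 0.95 cutoff. They take the DLT count as given, so the wording does not move them. By exact binomial calculation, the chance of a toxicity stop at the 10- or 20-patient look goes from 0.024 to 0.028–0.032 with other DLTs at 30%, and from 0.146 to 0.158–0.172 at 40%.

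**The case against.** The strongest reply is that this is a drafting slip whose answer the protocol already supplies. Section 4.1 cites 2.3.2, no section cites 11.1.1 for the definition, and Table 4 treats grade 4 as the end of obinutuzumab. The conflict needs a reaction that is grade 4, related, fully resolved within 24 hours and inside the 28-day window. A cohort summary goes to the IND Office before any dose change, so a case would probably be noticed. All of this stands and lowers the weight. It does not remove the conflict: the phrase in 11.1.1 is grammatical, does not look like an error, and sits in the operative rule.

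A second reply is that the criterion for a delay of more than two weeks would catch a patient stopped for good. It might, but it speaks of delay and does not say that permanent discontinuation is one.

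A third is that the event says little about the dose being tested. Obinutuzumab is fixed, and "Lenalidomide capsules will be taken orally daily each day on days 2 - 22", so a day 1 reaction precedes any lenalidomide. That is fair for day 1. Obinutuzumab is also infused on days 2, 8, 15 and 22, and the criterion does not separate the two drugs.

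The assumed rate is also open to challenge. The section 1.2.3 figures pool grades 3 and 4, do not require resolution within 24 hours, and come from other doses. This trial splits the first dose 100 mg/900 mg and gives steroids in cycle 1. That is why a range is shown.

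**Conclusion.** The inconsistency is real and should be corrected. As written, 11.1.1 leaves a related transient grade 4 reaction out of the phase I count, and section 4.1 with Table 4 shows that 2.3.2 has the intended wording. The average effect is small: 1.4 to 3.5 points on escalation per level at an assumed 1% to 2% rate. It is large only if the event occurs early at a level, where escalation is 0.709 against 0.328 (other DLTs at 20%).

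A reader might infer more than this, in four ways that the documents do not support.

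- *Patients are less protected under 11.1.1.* Section 6.1.1 and Table 4 apply whichever list is used.
- *The early-event contrast is wider, for example 0.804 against 0.328.* The 0.804 is (1−o)² + 2o(1−o)⁴ at o = 20%, which requires the affected patient to have no other DLT. Neither section states such a condition or says how a patient taken off treatment early is scored. Under independence the value is 0.709.
- *The chance of seeing such an event is 17% to 30%.* That uses the maximum of 18 patients; with 12 it is 11% to 22%.
- *The phase II design is wrong.* Its boundaries and sample size are unaffected, and the absence of a repeated DLT definition in 11.1.2 is only missing detail.

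**What to change.** In the infusion-reaction exception of section 11.1.1, replace *more* with *less*, so that it matches section 2.3.2. Optionally, add to section 11.1.2 that phase II DLT monitoring uses the section 2.3.2 definition. The cost is one word and, if wanted, one cross-reference. No patients, assessments, stopping boundaries or sample sizes change.
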